8.1.3 Quality of life assessment

All patients will be asked to fill in a questionnaire with QoL questions including the LARS-score, Decision Regret form, EORTC QLQ C30 and CR29 as well as additional questions derived from previous studies within rectal cancer (46). The time points for QoL questionnaire collection are the same as for the radiological follow-up:

1. Baseline
2. End of CRT treatment (at 2-3 months)
3. 1 year
4. 2 years
5. 3 years

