5 TRIAL DESIGN AND PROCEDURES

5.1 Overall trial design

The study design is a national multi-centre prospective non-randomized phase IV cohort study. Planned centres are Sahlgrenska University Hospital, Skåne University Hospital, Stockholm South General Hospital. It is an initiative from the surgical and oncological community in Sweden to offer patients a choice of treatment before solid scientific evidence is present to support either treatment option. It is a low-intervention clinical trial as the investigational medicinal product Capecitabine is authorized and used according to the terms in its marketing authorization to the same diagnosis but at a different tumour stage than standard. The complementary diagnostic procedures are not considered to contribute to the risk or burden to subject safety compared to normal clinical practice.

Patients who meet inclusion criteria will be offered neoadjuvant treatment to defer/avoid surgery or TME surgery upfront.

Those who prefer organ preservation will be treated with **mesorectal chemoradiotherapy**.

Those who prefer standard surgery or have no preference, will undergo standard TME surgery without neoadjuvant treatment. They will be asked to participate in the QoL part of the study, while the remainder of the data will be extracted from the national quality registry, the Swedish ColoRectal Cancer Registry (SCRCR)

For possible organ preservation long course concurrent chemoradiation will be performed (CRT):

Capecitabine: 825 mg/m² orally, b.d., on radiotherapy days

Radiotherapy: A dose of 50 Gy applied to the primary tumour and surrounding mesorectum in 25 fractions of 2 Gy, 5 days a week.

The **first assessment after treatment is at 6-8 weeks** (from end of chemoradiotherapy) using composite clinical, endoscopic and MRI based assessment will identify the minority of non-responders who should convert to TME surgery. Patients demonstrating a clinical complete response (cCR) after chemoradiotherapy 6-8 weeks will be offered to enter the national watch and wait program and followed accordingly in the WoW study NCT03125343 with endoscopy and MRI and clinical follow-up accordingly (at present 3, 6, 9, 12, 15, 18, 21 and 24 months and then every 6 months for another 3 years and then yearly for five more years).

If **near complete response** there will be a re-evaluation after **12 weeks** after chemoradiotherapy to determine if the criteria for clinical complete response (cCR) are met.

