5.2 Procedures and flow-chart

See table 1 for details on each visit.

Each follow-up visit may vary 2-3 weeks depending on availability to radiology, endoscopy and clinical visit.

Trial ID: NG-ST
Version No: 1.1
Date: 10 December 2025
EU Trial Number: 2025-522955-25-00

432

	Screening	Neoadjuvant treatment				Surgery if applicable ⁴		Follow-up				435
	At/before first visit in surgical clinic	First visit in oncology clinic	End of CRT treatment	6-8 weeks after end of neoadjuvant treatment if not cCR	10-12 weeks after end of neoadjuvant treatment if not cCR	Surgery	Hospital stay after surgery, follow-up 1 month after discharge	3 months after cCR	6 months after cCR	9 months after cCR	12 months after cCR or surgery	Every 3 months 12-24 months after cCR
Written informed consent	X											441
Medical history ¹	X											442
ECOG performance status	X		X									443
Digital rectal examination	X			X	X			X	X	X	X	X
Physical examination	X											444
Colonoscopy ²	X											445
Confirmed diagnosis of adenocarcinoma ³	X	X										446
Computerized Tomography (CT) scan thorax, and CT or MRI abdomen	X										X	447
High resolution MRI pelvis	X			X	X			X	X	X	X	448
MDT review	X											449
Blood sample	X					X						450
Preparation of FFPE tissue blocks and biopsies ³	X					X						451
QoL questionnaire	X			X							X	452
Toxicity related to (chemo)radiotherapy registered in CRF			X					X				453
Complications related to surgical procedure according to Clavien-Dindo												454
Sigmoidoscopy								X	X	X	X	X
Survival status		X	X				X	X				456

459
460
461
462

history includes details of current colorectal cancer, previous and current medical conditions and previous treatments received. ² Colonoscopy should be performed either prior surgery or within three months after surgery. At least one colonoscopy to be performed within the first 3 years of follow-up and according to national guidelines. ³ Biopsies taken and sent to routine pathology department (note name of pathology department in CRF). ⁴ Surgery can be performed either immediately or when a cCR cannot be achieved or if there is suspicion of regrowth.

Trial ID: NG-ST
Version No: 1.1
Date: 10 December 2025
EU Trial Number: 2025-522955-25-00

Follow-up

Not registered in eCRF but according to clinical routine

Not registered in eCRF but according to clinical routine

Not registered in eCRF but according to clinical routine

Not registered in eCRF but according to clinical routine

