	15 months after cCR	18 months after cCR	24 months after cCR or surgery	30 months after cCR	36 months after cCR or surgery	42 months after cCR	48 months after cCR	54 months after cCR	60 months after cCR
Written informed consent									
Medical history ¹									
ECOG performance status									
Digital rectal examination	X	X	X	X	X	X	X	X	X
Physical examination									
Colonoscopy ²									
Confirmed diagnosis of adenocarcinoma ³									
Computerized Tomography (CT) scan thorax, and CT or MRI abdomen			X		X		X		X
High resolution MRI pelvis	X	X	X	X	X	X	X	X	X
MDT review									
Blood samples			X		X				
Preparation of FFPE tissue blocks and biopsies ³									
QoL questionnaire			X	X	X				
Toxicity related to (chemo)radiotherapy registered in CRF			X		X				
Complications related to surgical procedure according to Clavien-Dindo									
Sigmoidoscopy	X	X	X	X	X	X	X	X	X
Survival status	X	X	X	X	X	X	X	X	X

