8.1.2 Secondary endpoints

Secondary outcome	Variable	Summary measure	Time point^o
Local recurrence	Registration in CRF	Proportion	3 years
Local regrowth	Registration in CRF	Proportion of patients that have achieved clinical complete response	1, 2 and 3 years
Surgical morbidity measured as Comprehensive Complications index^o	All complications registered according to Clavien-Dindo	Median value	90 days postoperatively in cases where surgery is necessary
Organ preservation rate at 3 years	Registration in CRF	Proportion	Patients with remaining rectum without deviating stoma at three years. Regardless of function.

Clinical complete response rate	Registration in CRF	Proportion	1 and 2- and 3-years follow-up after inclusion
R0 rate among operated patients	Registration in CRF	Proportion among operated patients	1 and 3 years after inclusion, both patients with initial organ preservation and TME resection surgery
Metastases	Registration in CRF	Proportion as well as subgroup specification of location	1 and 3 years after inclusion
Total length of hospital stay	Total number of days including readmissions	Median and range	Within 365 days after diagnosis
Quality of life	Measured in QoL questionnaire	Value baseline vs follow-up. Likert scale with dichotomization	Baseline, post treatment, at surgery if applicable and at one, two and three years
Urinary function	Measured in QoL questionnaire focus on incontinence, emptying difficulties and urgency	Value baseline vs follow-up and comparing groups	Baseline, post treatment, at surgery if applicable and at one, two and three years
Sexual function	Measured in QoL questionnaire, focus on both function and quality	Value baseline vs follow-up and comparing groups	Baseline, post treatment, at surgery if applicable and at one, two and three years
Bowel and stoma function	Measured in QoL questionnaire, major LARS	Value follow-up comparing groups	Baseline, post treatment, at surgery if applicable and at one, two and three years
Patients with a stoma	Measured as number of patients with a stoma/total number of patients	Proportion	One, two, three years
Health economic analysis	EQ5D as well as cost evaluation from both societal and health care sector perspective. Will include number of days on sick leave.		3 years after diagnosis
Mortality	Registration in CRF	Proportion	3 and 5 years after diagnosis
Patient satisfaction	Decision regret form		3 years after inclusion

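### The yearly patient-reported questionnaires have no single origin: Table 1 counts from complete response or surgery, other sections from diagnosis or inclusion, and the form at surgery is listed in only some places

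*Protocol*

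**What the plan says.** All references are to the protocol.

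- **Section 8.1.3** gives the questionnaire to all patients and states: "The time points for QoL questionnaire collection are the same as for the radiological follow-up". The list below it has baseline, the end of CRT (put at 2-3 months), and 1, 2 and 3 years. No origin is given for the years.
- **Section 5.2, Table 1** marks the questionnaire at screening, at 6-8 weeks after neoadjuvant treatment, and in the columns "12 months after cCR or surgery", "24 months after cCR or surgery" and "36 months after cCR or surgery". There is a further mark at 30 months after cCR, and none in the surgery or post-discharge columns. Footnote 4 covers immediate surgery, surgery because cCR is not reached, and surgery for suspected regrowth.
- **Section 5.1** lists the yearly case report form points as 1, 2 and 3 years from diagnosis. Of patients having upfront TME it says: "They will be asked to participate in the QoL part of the study".
- **Section 8.1.2** gives the patient-reported time points as "Baseline, post treatment, at surgery if applicable and at one, two and three years"; the synopsis says the same. For urinary and sexual function the summary is "Value baseline vs follow-up and comparing groups", and bowel and stoma function is also compared between groups. Decision Regret, which Section 8.1.3 makes part of the same questionnaire, is set at 3 years after inclusion.

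**The concern.** A yearly form can be sent on one date only. Sections 5.1, 5.2, 8.1.2 and 8.1.3 between them allow three origins: diagnosis, inclusion, and cCR or surgery. The third depends on how the patient responds. A patient having upfront TME starts the clock at an early operation, a responder starts it when cCR is declared, and a non-responder starts it at a later operation. A patient with cCR who is operated on for regrowth fits both halves of the column heading, and nothing says which half applies.

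Section 2.4 makes the upfront-TME patients the control arm, and function is to be compared between the groups. If the nominal 1-year form means different times since the treatment choice in the two groups, part of any difference reflects the schedule. Analysis cannot supply scores at a common time if the forms were not collected then, so this has to be settled in the protocol rather than in the analysis plan.

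**Working it through.** **Inputs from the protocol.** CRT lasts 5 weeks (Section 7.3.9). Response is first assessed 6-8 weeks after CRT, with re-evaluation of near complete response at 12 weeks (Section 5.1; Table 1 has 10-12 weeks). Visits may vary by 2-3 weeks (Section 5.2). One month is 365.25/12/7 = 4.35 weeks.

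**The plan's own figure.** Section 8.1.3 puts the second form at 2-3 months. From the start of CRT to the first assessment is 5 + 6 = 11 to 5 + 8 = 13 weeks, or 2.5-3.0 months, which agrees. Counted from the end of CRT it would be 6-8 weeks, or 1.4-1.8 months, which does not. So the early form fits a clock that starts at about baseline or CRT start, unlike the yearly columns of Table 1.

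**Responders on the Table 1 clock.** cCR is declared 5 + 6 = 11 to 5 + 12 = 17 weeks after CRT start, or 2.5-3.9 months. The form 12 months after cCR therefore falls 14.5-15.9 months after CRT start. An upfront-TME patient completes it 12 months after the operation. With equal waits from choice to first treatment, the offset is 2.5-3.9 months.

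**Unequal waits (assumed, not in the protocol).** Offset = (wait to CRT + 11 to 17 weeks − wait to TME) / 4.35. Take waits of 2-6 weeks to CRT and 2-8 weeks to TME:
- smallest: (2 + 11 − 8) = 5 weeks, 1.1 months
- largest: (6 + 17 − 2) = 21 weeks, 4.8 months

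**Non-responders.** With surgery 2-6 weeks after the assessment (assumed), the operation falls 11 + 2 = 13 to 17 + 6 = 23 weeks after CRT start. With equal initial waits, the form 12 months after surgery is then 3.0-5.3 months later than for upfront TME.

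**cCR, then regrowth surgery.** The timing of surgery is illustrative. Surgery clock = 2.5 to 3.9 + months from cCR to surgery + 12. On the cCR clock the form is 12 minus that interval after the operation.

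| Surgery after cCR | Surgery clock: months from CRT start | cCR clock: months after surgery |
|---|---|---|
| 3 months | 17.5-18.9 | 9 |
| 6 months | 20.5-21.9 | 6 |
| 9 months | 23.5-24.9 | 3 |
| 11 months | 25.5-26.9 | 1 |

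**On a common clock** from diagnosis or inclusion, the scheduled offset between groups in time from that origin is 0, apart from the 2-3 week window.

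**Form at surgery.** The synopsis and Section 8.1.2 list it. The list in Section 8.1.3 omits it, and Table 1 has no mark for it.

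**The case against.** The best defence is that Table 1 is only one reading. Section 5.1 counts years from diagnosis, Section 8.1.2 uses inclusion for Decision Regret, and on either clock the groups are aligned. The sentence in Section 8.1.3 introduces the list, and the listed years coincide with the yearly imaging in Table 1. Timing from the end of treatment or from surgery can also be defended. These are secondary outcomes in a non-randomised cohort that is analysed descriptively. All of this stands. It limits the point to a contradictory origin and does not settle which origin a site should use.

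A reader might infer more than the documents support:

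- *That upfront-TME patients have no radiological follow-up.* Table 1 marks CT and pelvic MRI in the yearly columns that include surgery, and footnote 4 includes immediate surgery. What these patients lack is the 3-monthly watch-and-wait imaging.
- *That the period around salvage surgery goes unmeasured.* The synopsis and Section 8.1.2 list a form at surgery. It would not capture recovery afterwards, but the defect shown is that the sections disagree.
- *That the timing favours organ preservation.* On the Table 1 clock a non-responder is measured 12 months after surgery, exactly as after upfront TME. A responder's extra time since the end of CRT is 6-12 weeks (1.4-2.8 months), because 5 of the 11-17 weeks are treatment. On the cCR clock a patient with regrowth may be measured soon after surgery, which works against organ preservation. Section 3.2 also names late radiotherapy effects.
- *That the bias can be given in score points.* The protocol states neither the share of patients having regrowth surgery nor the drop in scores after it.

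The 30-month mark should be checked on the laid-out table, since cells may have shifted in the text available here. The point does not depend on it.

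**Conclusion.** The point holds as a contradiction about the origin of the yearly forms and about the form at surgery. A response-dependent schedule is what follows if Table 1 is applied; it is not established as the sponsor's intention. In that case the 1-year form of responders is 2.5-3.9 months late relative to upfront TME when initial waits are equal, and about 1.1-4.8 months late under the assumed unequal waits. This exceeds the 2-3 week visit window. For regrowth surgery 9 months after cCR, the two possible dates are 9 months apart: 14.5-15.9 or 23.5-24.9 months after CRT start. The direction and size of any bias in scores are not established. The primary endpoint is not affected. The protocol should be amended on this point, preferably before yearly forms are sent out.

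**What to change.** 1. In Section 8.1.3, delete the sentence that equates questionnaire times with the radiological follow-up.
2. State one origin for both groups. Inclusion is a natural choice because Section 8.1.2 already uses it for several endpoints. Send the forms at 12, 24 and 36 months from that date, whatever happens with cCR, regrowth or surgery.
3. Put the questionnaire row of Table 1 on the same clock. Remove the 30-month mark or apply it to both groups.
4. Decide whether there is a form at surgery, and make the synopsis, Section 8.1.2, Section 8.1.3 and Table 1 agree.
5. Forms timed from surgery may be kept as additional descriptive data.

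The cost is mainly wording. Section 14.2 already has the study secretariat administering the postoperative questionnaires, so sending forms by date should be feasible. A form may no longer coincide with a clinic visit, which is a small price. No treatment or clinical follow-up changes.

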Primary endpoint:	Clinical complete response rate evaluated by MRI and endoscopy at one year (i.e. patients that have not undergone surgery)
Secondary endpoint:	
 • Oncologic: 
 ○ Clinical complete response rate without surgical intervention at three years ○ Local recurrence at three years ○ Mortality at three years ○ Overall survival at three years • Surgical 
 ○ Surgical morbidity measured as Comprehensive Complications index at 90 days after surgery (if performed) ○ Total length of hospital stay during the first year ○ Outcome after surgery (Histopathological assessment of the resected rectal specimen to report (a) Presence of clear margins (>1mm from excision border to tumour edge), (b) TNM staging.) • Patient reported outcomes (all measured Baseline, post treatment, at surgery if applicable and at one, two and three years) 
 ○ Quality of life ○ Urinary function ○ Sexual function ○ Bowel and stoma function 
Health economic analysis at three years

Trial design:	
National, multi-centre, open-label, prospective trial.
 
Patients will choose possible organ preservation or standard surgery.
 
Those who prefer possible organ preservation will be offered treatment according to the experimental arm of the STAR TREC trial: mesorectal Chemoradiotherapy (CRT).
 
Those who prefer standard surgery or have no preference will undergo standard Total Mesorectal Excision (TME) surgery without neoadjuvant radiotherapy treatment.

Trial population:	Subjects referred to either a colorectal surgeon or the colorectal cancer multidisciplinary team (MDT) with suspected early stage rectal cancer (T1-T3bNx/N0). Diagnosis must be confirmed with a biopsy prior to study entry.
Number of subjects:	Due to the study design the number of patients to be included has not been fixed, but it is estimated to be at least 60-80 patients during the period until STAR-TREC data will be available
Inclusion criteria:	
 • Biopsy proven adenocarcinoma of the rectum < 12 cm • Magnetic Resonance Imaging (MRI)-staged TT1-3b, N0, MX/M0 rectal tumour • MDT determines that the following treatment options are all

	
reasonable and feasible: TME surgery or CRT
 
 • Eastern Cooperative Oncology Group (ECOG) performance status 0-1 • Willing and able to consent

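### Two conflicting questionnaire schedules: under one, the upfront-TME control group has no patient-reported measurement between baseline and one year; under the other, its early point is undefined

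*Protocol*

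**What the plan says.** Section 2.4 makes patients who choose upfront TME the control arm. Section 5.1 says of them: "They will be asked to participate in the QoL part of the study". Their remaining data come from the national colorectal cancer registry.

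The questionnaire schedule is stated in four places.

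- **Synopsis, secondary endpoints:** patient-reported outcomes are "all measured Baseline, post treatment, at surgery if applicable and at one, two and three years".
- **Section 8.1.2:** the quality-of-life, urinary, sexual and bowel/stoma rows repeat this: "Baseline, post treatment, at surgery if applicable and at one, two and three years". The urinary and sexual rows give the summary measure as "Value baseline vs follow-up and comparing groups". The bowel/stoma row also compares groups at follow-up. The general quality-of-life row compares baseline with follow-up and mentions no group comparison.
- **Section 8.1.3:** "All patients will be asked to fill in a questionnaire with QoL questions". The list is baseline, "End of CRT treatment (at 2-3 months", and 1, 2 and 3 years. There is no entry at or after surgery.
- **Table 1 (section 5.2), as extracted:** questionnaire marks in the first year stand at screening, in the column "6-8 weeks after end of neoadjuvant treatment if not cCR", and in the column "12 months after cCR or surgery". There is none in the two surgery columns.

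Section 14.2 mentions postoperative questionnaires sent by the study secretariat but gives no time for them.

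**The concern.** A patient who goes straight to TME has no end of CRT and no visit after neoadjuvant treatment. A site that follows 8.1.3 or Table 1 therefore has no occasion to give that patient a questionnaire until one year, while a CRT patient is measured in the early post-treatment period. A site that follows the synopsis or 8.1.2 would do something else, and would have to guess what *post treatment* means for someone whose treatment is surgery.

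The early months matter for this comparison. Section 3.1 names avoided surgical complications, possibly better bowel function and avoidance of a stoma as the benefits of organ preservation. Section 2.1 describes leakage, temporary stomas, and urinary, sexual and bowel dysfunction after TME. If the control group is first measured again at one year, the early patient-reported burden of surgery is not seen, while that of CRT is. A questionnaire that was never sent cannot be recovered in the analysis.

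**Working it through.** The plan has no figure to reproduce here. The check sets the four statements side by side and counts the questionnaire points between baseline and one year that each group can reach.

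| Source | Early points listed | CRT patient | Upfront-TME patient |
|---|---|---|---|
| Synopsis | post treatment; at surgery if applicable | 1, or 2 if later operated | 1 (at surgery), or 2 if *post treatment* also covers surgery |
| 8.1.2 | same as synopsis | 1, or 2 if later operated | 1 or 2, as above |
| 8.1.3 | end of CRT (at 2-3 months) | 1 | 0 |
| Table 1, as extracted | 6-8 weeks after neoadjuvant treatment | 1 | 0 |

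**Step 1: is the 2-3 months in 8.1.3 a calendar point for everyone?** CRT lasts 5 weeks (section 7.3.9). Adding the 6-8 weeks of the marked Table 1 column gives 5 + 6 = 11 to 5 + 8 = 13 weeks, or about 2.5 to 3 months from the start of CRT. The bracket therefore fits a date counted from CRT. Section 8.1.3 also says that questionnaires follow the radiological follow-up. In Table 1 the early pelvic MRI marks stand in the post-neoadjuvant and post-cCR columns, with none in the surgery columns. No origin is given from which a TME patient could count 2-3 months.

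**Step 2: does the synopsis and 8.1.2 schedule give the control group a usable early point?** It has two candidates.

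- *At surgery*: for an upfront-TME patient this follows soon after baseline and comes before any postoperative effect. It does not record what the comparison needs.
- *Post treatment*: this is not defined for a patient whose treatment is surgery. The only place that spells out an early time is 8.1.3, and it does so in terms of CRT.

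**Step 3: which comparisons depend on it?** Three outcomes in 8.1.2 list *post treatment* among their times and compare groups: urinary function, sexual function, and bowel/stoma function. Their one-, two- and three-year points exist for both groups.

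**Side observations for the reconciliation, from the extracted Table 1.** The marked early column is headed as applying to patients without cCR, although section 5.1 sends every CRT patient to the 6-8 week assessment. A 30-month questionnaire mark appears in none of the three text schedules. The 12-month column counts from cCR or surgery, while 8.1.3 gives bare years.

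**The case against.** The strongest reply is that the control group is not left unmeasured at all. The synopsis and 8.1.2 schedule questionnaires after treatment and at surgery, section 14.2 speaks of postoperative questionnaires, and 8.1.3 addresses all patients and gives a time in months. This stands in part. A reader might infer from 8.1.3 alone that the sponsor chose never to observe the early postoperative period. The documents do not support that: they contradict each other, and one of the two schedules does intend more. The reply does not remove the problem, because neither schedule gives the control group a defined questionnaire after surgery and before one year.

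A second reply is that Table 1 is damaged in extraction; its surgical complications row, for example, carries no mark in any column. That is a fair reason to give absent marks little weight. The list in 8.1.3 does not depend on them.

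A third reply is that the groups are self-selected, the statistics are descriptive, and the yearly points are common to both. This limits the damage to the early part of three secondary comparisons.

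A stronger reading is also tempting: that the health-economic result is biased against CRT by a definite amount. If an equal utility dip d were recorded only in the CRT group at time t in year 1, the trapezoid rule would charge that group d·t/2 + d·(1−t)/2 = d/2, and the TME group nothing. But the size of d, its equality in both groups, recovery by one year and the interpolation are all assumptions. The health-economic row of 8.1.2 names EQ5D, costs and sick leave, with no QALY, no interpolation and no group contrast. EQ5D is not among the instruments named in 8.1.3, so its timing is unknown. Sick leave, and hospital days including readmissions within 365 days, capture part of the early burden of surgery. No QALY figure or direction of bias should be claimed.

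**Conclusion.** The concern holds as an internal contradiction with a practical consequence. Under 8.1.3 and Table 1 as extracted, the control group has 0 defined questionnaires between baseline and one year against 1 in the CRT group. Under the synopsis and 8.1.2 it has at least one, but that one precedes the postoperative period or is undefined. Either way, the early comparison of urinary, sexual and bowel/stoma function has no matched control data. An EQ5D utility analysis that used these times would be exposed in the same way, by an amount the protocol does not allow one to state.

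The conclusion rests on reading the second item of 8.1.3 as tied to CRT, as its own label says. It does not touch the primary endpoint or the yearly comparisons. It should be corrected before recruitment, because the missing data could not be recreated later.

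**What to change.** - In 8.1.3, replace the second item by one early questionnaire sent to both groups at the same time from a common origin. Suggested wording: *Early questionnaire, N weeks after inclusion, both groups.* N should be set so that it falls after CRT and after upfront TME. The protocol gives the length of CRT but not the waiting times to CRT or surgery, so the sponsor must choose N from the centres' own figures.
- Use that same point to define *post treatment* in the synopsis and 8.1.2, and mark it in Table 1 for both groups.
- State in all four places whether a questionnaire at surgery exists and, if so, for whom. Settle the 30-month mark and the origin of the yearly points at the same time, and say when EQ5D is collected.
- Keep questionnaires completed after surgery for incomplete response or regrowth in the CRT-strategy group. That surgery is part of what the strategy costs the patient, and leaving it out would favour CRT.

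The cost is a protocol wording change and about one extra mailed questionnaire per TME patient, sent by the secretariat that already handles the mailings. One limitation remains: at a fixed time from inclusion, the two groups are at different distances from the end of their treatment, so treatment dates should be reported with the result. No treatment rule changes.
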